5.7.1 Contraception

One of the highly effective methods of contraception listed below is required during study duration and until the end of relevant systemic exposure, defined as 6 months after the end of study treatment.*

Highly Effective Contraceptive Methods That Are User Dependent

Failure rate of <1% per year when used consistently and correctly.^a

- Combined (estrogen- and progestogen-containing) hormonal contraception associated with inhibition of ovulation^b
 - oral
 - intravaginal
 - transdermal
- Progestogen-only hormonal contraception associated with inhibition of ovulation^b
 - oral
 - injectable

Highly Effective Methods That Are User Independent

- Implantable progestogen-only hormonal contraception associated with inhibition of ovulation ^b
- Hormonal methods of contraception including oral contraceptive pills containing a combination of estrogen and progesterone, vaginal ring, injectables, implants and intrauterine hormone-releasing system (IUS)^c
- Intrauterine device (IUD)^c
- Bilateral tubal occlusion
- Vasectomized partner

A vasectomized partner is a highly effective contraception method provided that the partner is the sole male sexual partner of the WOCBP and the absence of sperm has been confirmed. If not, an additional highly effective method of contraception should be used.

Sexual abstinence

Sexual abstinence is considered a highly effective method only if defined as refraining from heterosexual intercourse during the entire period of risk associated with the study drug. The reliability of sexual abstinence needs to be evaluated in relation to the duration of the study and the preferred and usual lifestyle of the participant.

- It is not necessary to use any other method of contraception when complete abstinence is elected.
- WOCBP participants who choose complete abstinence must continue to have pregnancy tests, as specified in **Section 10**.
- Acceptable alternate methods of highly effective contraception must be discussed in the event that the WOCBP participants chooses to forego complete abstinence

NOTES:

- ^a Typical use failure rates may differ from those when used consistently and correctly. Use should be consistent with local regulations regarding the use of contraceptive methods for participants participating in clinical studies.
- Hormonal contraception may be susceptible to interaction with the study drug, which may reduce the efficacy of the contraceptive method. Hormonal contraception is permissible only when there is sufficient evidence that the IMP and other study medications will not alter hormonal exposures such that contraception would be ineffective or result in increased exposures that could be potentially hazardous. In this case, alternative methods of contraception should be utilized.
- ^c Intrauterine devices and intrauterine hormone releasing systems are acceptable methods of contraception in the absence of definitive drug interaction studies when hormone exposures from intrauterine devices do not alter contraception effectiveness

Unacceptable Methods of Contraception*

- Male or female condom with or without spermicide. Male and female condoms cannot be used simultaneously
- Diaphragm with spermicide
- Cervical cap with spermicide
- Vaginal Sponge with spermicide
- Progestogen-only oral hormonal contraception, where inhibition of ovulation is not the primary mechanism of action
- Periodic abstinence (calendar, symptothermal, post-ovulation methods)
- Withdrawal (coitus interruptus).
- Spermicide only
- Lactation amenorrhea method (LAM)
 - * Local laws and regulations may require use of alternative and/or additional contraception methods.

CONTRACEPTION GUIDANCE FOR MALE PARTICIPANTS WITH PARTNER(S) OF CHILD BEARING POTENTIAL.

Male participants with female partners of childbearing potential are eligible to participate if they agree to the following during the treatment and until the end of relevant systemic exposure.

- Inform any and all partner(s) of their participation in a clinical drug study and the need to comply with contraception instructions as directed by the investigator.
- Male participants are required to use a condom for study duration and until end of relevant systemic exposure defined as 6 months after the end of study treatment.
- Female partners of males participating in the study to consider use of effective methods of contraception until the end of relevant systemic exposure, defined as 6 months after the end of treatment in the male participant.
- Male participants with a pregnant or breastfeeding partner must agree to remain abstinent from penile vaginal intercourse or use a male condom during each episode of penile penetration during the treatment and until 6 months after the end of study treatment.
- Refrain from donating sperm for the duration of the study treatment and until 6 months after the end of study treatment.

5.7.2 Use in Pregnancy

The investigational agents used in this protocol may have adverse effects on a fetus; therefore, women with a positive pregnancy test at screening will not be eligible for enrollment. If a subject inadvertently becomes pregnant while on treatment, the subject will immediately be removed from the study. The site will contact the subject at least monthly and document the subject's status until the pregnancy has been completed or terminated

Pregnancy in female subjects or in partners of male subjects throughout the study or within 6 months of completing treatment should be reported initially as a serious adverse event (see reporting procedures in **Section 7.5.6**) by the investigator within 24 hours of learning of its occurrence. Pregnancy information must be reported on the Pregnancy Form.

Protocol required procedures for study discontinuation and follow-up must be performed on the subject unless contraindicated by pregnancy (e.g., x-ray studies). Other appropriate pregnancy follow-up procedures should be considered if indicated.

Follow-up information regarding the course of the pregnancy, including any voluntary or spontaneous termination, perinatal and neonatal outcome and where applicable, offspring information must be reported on the Pregnancy Follow-up Form. Pregnancy outcomes must also be collected for the female partners of any males in this trial. Consent to report information regarding these pregnancy outcomes should be obtained from the female partner.

5.7.3 Use in Nursing Women

Since many drugs are excreted in human milk, and because of the potential for serious adverse reactions in the nursing infant, subjects who are breast-feeding are not eligible for enrollment.

5.7.4 All Subjects (Male and Female)

All sexually active patients must use at least a barrier method (i.e., condom) to prevent transmission of body fluids.

5.8 **Duration of Therapy**

Subjects who are clinically stable and meet dosing requirements (per Section 6.2) may continue to receive treatment until the criteria in Section 5.9 are met.

5.9 Criteria for Removal from Treatment

The reason for study removal and the date the subject was removed will be documented in the CRF.

A subject will be discontinued from the trial for any of the following reasons:

• The subject or legal representative (such as a parent or legal guardian) withdraws consent for participation in the study.

A subject must be discontinued from treatment (but may continue to be monitored in the post-treatment follow-up portion of the trial) for any of the following reasons:

- The subject or legal representative (such as a parent or legal guardian) withdraws consent for treatment.
- Intercurrent illness that prevents further administration of treatment,
- Unacceptable toxicity (see **Section 5.6**). Exceptions for treatment discontinuation are listed in **Section 5.6**,
- Disease progression as defined in **Section 5.9.1**,
- Severe or life-threatening retifanlimab-related AE(s) (see Section 6.2),
- Need for >2 dose delays due to the same drug-related toxicity as per the dose delay guidelines (see **Section 6.2**),
- If, in the opinion of the Investigator, a change or temporal or permanent discontinuation of therapy would be in the best interest of the subject.
- Noncompliance with trial treatment or procedure requirements,
- Subject is lost to follow-up, or
- Subject becomes pregnant.

A subject may, at the discretion of the Investigator, be discontinued from treatment (but may continue to be monitored in the post-treatment follow-up portion of the trial) if they have:

- Completed 6 months of treatment with retifanlimab and has a complete response (CR) by at least two scans ≥ 4 weeks apart AND have received at least two doses of retifanlimab beyond the initial determination of CR.
- Completed 24 months of treatment with retifanlimab and has a response of stable disease, partial response, or complete response at the time of discontinuation

Note: time on treatment is calculated from the date of first dose.

5.9.1 Disease Progression

Retifanlimab is expected to trigger immune-mediated responses, which require activation of the immune system prior to the observation of clinical responses. Such immune activation may take weeks to months to be evident. Some subjects may have objective volume increase of tumor lesions or other disease parameters within weeks following the start of immunotherapy. Such subjects may not have had sufficient time to develop the required immune activation or, in some subjects, tumor volume or other disease parameter increases may represent infiltration of lymphocytes into the original tumor. In conventional studies, such tumor volume or relevant laboratory parameter increases during the first 2-4 months of the study would constitute disease progression and lead to discontinuation of imaging to detect response, thus disregarding the potential for subsequent immune-mediated clinical response.

Subjects will be permitted to continue with treatment beyond initial RECIST 1.1 defined PD as long as they meet the following criteria:

- Investigator-assesses that the patient is not clinically deteriorating, and
- Subject is tolerating study drug.

The assessment of lack of deterioration should take into account whether the subject is clinically stable or if they unlikely to receive further benefit from continued treatment. The following criteria need to be taken into consideration:

- No significant decline in ECOG performance status.
- Absence of rapid progression of disease or of progressive tumor at critical anatomical sites (e.g., cord compression) requiring urgent alternative medical intervention.

All decisions to continue treatment beyond PD must be discussed with the IND Sponsor and documented in the study records.

Tumor assessments will be made using RECIST 1.1 (**Appendix B**) and iRECIST (**Appendix C**).

5.9.2 Retreatment with Retifanlimab

Patients who stop retifanlimab with SD or better may be eligible for resume therapy if they progress after stopping retifanlimab and they meet the following criteria:

EITHER

• Stopped initial treatment with retifanlimab after attaining an investigator determined confirmed CR according to RECIST 1.1, was treated for at least 6 months with retifanlimab, and received at least two doses of retifanlimab beyond the date when the initial CR was declared.

OR

• Subject had SD, PR or CR and stopped retifanlimab treatment after 24 months of study drug for reasons other than disease progression or intolerability

AND

- Experienced an investigator-determined confirmed radiographic or clinical disease progression after stopping their initial treatment with retifanlimab
- Did not receive any anti-cancer treatment since the last dose of retifanlimab
- Have an ECOG performance status of 0-2
- Female subject of childbearing potential should have a negative urine or serum pregnancy test within 3 days prior to receiving retreatment with study medication.
- Female subjects of childbearing potential should be willing to follow instructions for method(s) of contraception or abstain from heterosexual activity for the course of the study through 6 months after the last dose of study drug.
- Male subjects should agree to use an adequate method of contraception starting with the first dose of study therapy through 6 months after the last dose of study therapy.
- Does not have a history or current evidence of any condition, therapy, or laboratory abnormality that might interfere with the subject's participation for the full duration of the trial or is not in the best interest of the subject to participate, in the opinion of the treating investigator.

Subjects who restart treatment should resume at the next cycle which they would have received prior to discontinuation. Study visit requirements are outlined in the Study Calendar (Section 10.0).

5.10 End of Treatment (EOT) Visit

All subjects will return to the study site 28 days (\pm 7 days) after the final study treatment for an EOT evaluation. Procedures and assessments performed at these visits and beyond should follow the respective guidelines described in **Sections 5.11 and 10.0** as appropriate.

If the EOT visit occurs early (e.g., 1 week prior to the expected visit as protocol allows) or if the patient cannot return due to disease progression, an assessment for AEs should be made by telephone or email on day 28 (± 1 day) after last dose of study drug and documented.

For subjects who discontinue study drug after 24 months of SD or better or with a CR after 6 months (see Section 5.9.2), the EOT visit should be completed as described above. If a patient later restarts study drug, they should have a second EOT visit performed when they eventually discontinue study drug for a second time.

5.11 Duration of Follow-Up

5.12.1 Safety Follow-up

Subjects who discontinue treatment should be contacted by telephone or email at 90 days (+14 day reporting window) from their last dose of study drug or within 7 days before initiation of a new antineoplastic treatment (whichever comes first) to assess for treatment related toxicities. In addition, all SAEs occurring during this time should be reported as well.

Subjects who are discontinued from the study treatment due to an unacceptable drugrelated AE will be monitored for safety until the resolution of the AE to \leq grade 1 or stabilization or until initiation of a new therapy for their cancer, whichever occurs first.

5.12.2 Clinical Follow-up

Subjects who discontinue treatment without disease progression should continue to be monitored for disease status by radiologic imaging. Disease monitoring should continue to be assessed every two months (\pm 2 weeks) for the first 2 years and then every 3 months (\pm 4 weeks) until: 1) start of a new antineoplastic therapy (information of the new cancer therapy will be collected), 2) disease progression, 3) death, 4) withdrawal of consent, or 5) study closure, whichever occurs first.

5.12.3 Survival Follow-up

Subjects who discontinue treatment and have disease progression will enter the survival follow-up portion of the trial. Subjects should be contacted every 12 weeks (\pm 2 weeks) to monitor overall survival. Information of other cancer therapies after discontinuation from the study treatment will be collected as well.

6. DOSE MODIFICATION, DELAYS AND TOXICITY MANAGEMENT GUIDELINES FOR IMMUNE-RELATED AES

6.1 Dose Modifications

[figure not shown]
Subjects will be monitored continuously for AEs while on study drug. Subjects will be instructed to notify their physician immediately for any and all AEs. Dose escalations or reductions of retifanlimab will not be allowed.

6.2 Dose Delays and Discontinuation

Adverse events of a potential immunologic etiology, or irAEs, may be defined as AEs of unknown etiology, associated with drug exposure and consistent with an immune phenomenon. Immunerelated AEs may be predicted based on the nature of the compounds, their mechanism of action, and reported experience with immunotherapies that have a similar mechanism of action. Special attention should be paid to AEs that may be suggestive of potential irAEs. An irAE can occur shortly after the first dose or several months after the last dose of treatment. If an irAE is suspected,

efforts should be made to rule out neoplastic, infectious, metabolic, toxin or other etiologic causes before labeling an AE as an irAE.

Recommendations for management of specific immune-mediated AEs known to be associated with other PD-1 inhibitors (e.g., pembrolizumab, nivolumab) are detailed in **Table 4** (below). Algorithms for evaluation of selected immune toxicities that have previously been attributed to PD-1 inhibitors and management guidelines for irAEs not detailed elsewhere in the Protocol should follow the ASCO or ESMO Clinical Practice Guidelines (Brahmer et al 2018, Haanen et al 2017).

7. ADVERSE EVENTS: LIST AND REPORTING REQUIREMENTS

This study will use the descriptions and grading scales found in the revised CTCAE version 5.0 for AE reporting that can be found at

http://ctep.cancer.gov/protocolDevelopment/electronic applications/ctc.htm.

Information about all AEs, whether volunteered by the subject, discovered by investigator questioning, or detected through physical examination, laboratory test or other means, will be collected, recorded, and followed as appropriate.

7.1 **Definitions**

7.1.1 Adverse Event

An AE is defined as any undesirable sign, symptom or medical condition occurring after starting the study drug (or therapy) even if the event is not considered to be related to the study. An undesirable medical condition can be symptoms (e.g., nausea, chest pain), signs (e.g., tachycardia, enlarged liver) or the abnormal results of an investigation (e.g., laboratory findings, electrocardiogram). Medical conditions/diseases present before starting the study treatment are only considered AEs if they worsen after starting the study treatment (any procedures specified in the protocol). New medical conditions / diseases occurring before starting the study treatment but after signing the informed consent form will not be recorded as AEs. Additionally, expected progression of the disease being studied will not be recorded as an adverse event.

Laboratory abnormalities: Laboratory abnormalities present at the screening visit will be recorded as pre-treatment signs and symptoms. After study treatment administration, all grade 3 and 4 clinical laboratory results that represent an increase in severity from baseline will be reported as AEs. A grade 1 or 2 clinical laboratory abnormality should be reported as an AE only if it is considered clinically significant by the investigator (induce clinical signs or symptoms or require therapy), meets the definition of an SAE, or requires the participant to have study drug discontinued or interrupted..

7.1.2 Serious Adverse Event

A SAE is an undesirable sign, symptom or medical condition which:

- Results in death
- Is life threatening (defined as an event in which the subject was at risk of death at the time of the event; it does not refer to an event which hypothetically might have caused death if it were more severe)
- Requires inpatient hospitalization or causes prolongation of existing hospitalization (see note below for exceptions) for >24 hours
- Results in persistent or significant disability/incapacity
- Is a congenital anomaly/birth defect (note: reports of congenital anomalies/birth defects must also be reported on the Pregnancy Form)
- Is an important medical event (defined as a medical event(s) that may not be immediately life-threatening or result in death or hospitalization but, based upon

appropriate medical and scientific judgment, may jeopardize the subject or may require intervention [e.g., medical, surgical] to prevent one of the other serious outcomes listed in the definition above.) Examples of such events include, but are not limited to, intensive treatment in an emergency room or at home for allergic bronchospasm; blood dyscrasias or convulsions that do not result in hospitalization.)

- Potential drug induced liver injury (DILI) is also considered an important medical event.
- Is a new cancer (that is not a condition of the study)
- Is associated with an overdose
- Is a pregnancy or pregnancy outcome of spontaneous abortion, missed abortion, benign hydatidiform mole, blighted ovum, fetal death, intrauterine death, miscarriage, or stillbirth.

Events **not** considered to be SAEs are hospitalizations for:

- Admissions as per protocol for a planned medical/surgical procedure or to facilitate a procedure
- Routine health assessment requiring admission for baseline/trending of health status (e.g., routine colonoscopy)
- Medical/surgical admission for purpose other than remedying ill health state and was planned prior to entry into the study. Appropriate documentation is required in these cases.
- Admission encountered for another life circumstance that carries no bearing on health status and requires no medical/surgical intervention (e.g., lack of housing, economic inadequacy, care-giver respite, family circumstances, administrative).
- Admissions for monitoring of treatment-related infusion reactions that do not otherwise meet the criteria for a SAE.

7.2 Assessment of Causality

The relationship of an AE to the administration of the study drug is to be assessed by the investigator according to the following definitions:

- No (unrelated, not related, no relation): The time course between the administration of study drug and the occurrence or worsening of the adverse event rules out a causal relationship and another cause (concomitant drugs, therapies, complications, etc.) is suspected.
- Yes (related): The time course between the administration of study drug and the occurrence or worsening of the adverse event is consistent with a causal relationship and no other cause (concomitant drugs, therapies, complications, etc.) can be identified.

The following factors should also be considered:

• The temporal sequence from study drug administration - The event should occur after the study drug is given. The length of time from study drug exposure to event should be evaluated in the clinical context of the event.

- Underlying, concomitant, intercurrent diseases Each report should be evaluated in the context of the natural history and course of the disease being treated and any other disease the subject may have.
- Concomitant medication The other medications the subject is taking or the treatment the subject receives should be examined to determine whether any of them might be recognized to cause the event in question.
- Known response pattern for this class of study drug Clinical and/or preclinical data may indicate whether a particular response is likely to be a class effect.
- Exposure to physical and/or mental stresses The exposure to stress might induce adverse changes in the recipient and provide a logical and better explanation for the event.
- The pharmacology and pharmacokinetics of the study drug The known pharmacologic properties (absorption, distribution, metabolism, and excretion) of the study drug should be considered.

Assessment of Grade:

The investigator will make an assessment of grade for each AE and SAE reported during the study, which will be recorded in the CRF. The assessment will be based on the National Cancer Institute's CTCAE (Version 5.0) and graded as shown below:

- Grade 1: Mild; asymptomatic or mild symptoms; clinical or diagnostic observations only; intervention not indicated
- Grade 2: Moderate; minimal, local or noninvasive intervention indicated; limiting ageappropriate instrumental activities of daily living
- Grade 3: Severe or medically significant but not immediately life-threatening; hospitalization or prolongation of hospitalization indicated; disabling; limiting self-care activities of daily living
- Grade 4: Life-threatening consequences; urgent intervention indicated
- Grade 5: Death related to AE

Any AE that changes in grade during its course will be recorded in the CRF at the highest level experienced by the subject.

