5.6 Unacceptable Toxicity

Toxicities are defined in the Investigator's Brochure and **Table 4**. Unacceptable toxicities for this protocol that will trigger additional review described below are defined as:

- 1. Any treatment-related > grade 3 AEs. Exceptions include:
 - Asymptomatic laboratory abnormalities (AST, ALT, and bilirubin abnormalities requiring discontinuation as per **Table 4** will be considered unacceptable toxicity)
 - Grade 3 fatigue
 - Grade 3 dermatologic AEs that are considered mild in severity but only considered grade 3 because of >30% body surface involvement including pruritus
 - Diarrhea, nausea, or vomiting that resolves to < grade 3 within 48 hours of maximal intervention
 - Grade 3-4 hyperglycemia or grade 3 endocrinopathies where symptoms are controlled on hormone replacement therapy
- 2. Treatment related blood bilirubin > 5 x ULN or concurrent blood bilirubin > 2 x ULN and AST or ALT > 3 x ULN
- 3. Treatment related eye pain ≥ grade 2 or reduction of visual acuity that does not respond to topical therapy and does not improve to ≤ grade 1 severity within 2 weeks of starting therapy, or requires systemic therapy is an unacceptable toxicity.

Unexpected Grade 3 or greater laboratory abnormalities should be repeated within 24-72 hours if clinically indicated and monitored as necessary to determine if event meets toxicity criteria.

The proportion of treated subjects with unacceptable toxicity will be monitored using a Bayesian stopping guideline. A Beta (1.5, 5.5) prior, representing a toxicity rate of 21%, a slightly conservative estimate, was used in the development of our guidelines. We will halt the accrual and re-evaluate the safety if the posterior probability that the toxicity rate exceeds the 33% boundary is greater than 60%. Toxicity will be monitored continuously. **Table 2** summarizes the stopping boundaries for unacceptable toxicities.

Table 2. The number of unacceptable toxicities needed to trigger stopping guidelines throughout the course of the study.

Number of Subjects	Number of unacceptable toxicities needed to trigger re-evaluation
2	2
3-5	3
6-7	4
5-10	5
11-13	6
14-16	7
17-19	8
20-22	9
23-25	10

Table 3. Probability of triggering a re-evaluation based upon the proportion with an unacceptable toxicity for a range of true toxicity probabilities.

True probability of	Probability of triggering
unacceptable toxicity	stopping guidelines
5%	0.4%
10%	1.8%
15%	6%
20%	14%
25%	27.5%
30%	44.9%
35%	62.3%
40%	78%

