7.5.8.1 Expedited IND Safety Reports

7 Calendar-Day Telephone or Fax Report:

The IND Sponsor is required to notify the FDA of any fatal or life-threatening adverse event that is unexpected and assessed by the investigator to be possibly

related to the investigational agent. Such reports are to be emailed to the regulatory project manager and faxed [contact]) to the FDA within 7 calendar days of first learning of the event. Follow-up information will be submitted to the FDA as soon as relevant information is available.

15 Calendar-Day Written Report:

The IND Sponsor is required to notify the FDA of any SAE that is unexpected and related to the investigational agent in a written IND Safety Report.

Written IND Safety Reports should include an Analysis of Similar Events in accordance with regulation 21 CFR § 312.32. All safety reports previously filed with the IND concerning similar events should be analyzed. The new report should contain comments on the significance of the new event in light of the previous, similar reports.

Written IND safety reports with Analysis of Similar Events are to be submitted to the FDA within 15 calendar days of first learning of the event. Follow-up information will be submitted to the FDA as soon as relevant information is available.

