13.4 Safety monitoring and stopping guidelines

Adverse events will be monitored during the trial. The occurrence of unacceptable AEs, as defined in **Section 5.6**, at any time during the treatment will be the endpoint for safety monitoring. If the events of unacceptable AEs appear to be higher than 33%, we will temporarily halt the study pending safety evaluation. A Beta (1.5, 5.5) prior, representing a toxicity rate of 21%, a slightly conservative estimate, was used in the development of the stopping guidelines. The therapy will be re-evaluated if the posterior probability that the toxicity rate exceeds the 33% boundary is greater than 60%. **Table 5** summarizes the stopping boundaries for unacceptable toxicities.

Table 5. The number of unacceptable toxicities needed to trigger stopping guidelines throughout the course of the study.

Number of Subjects	Number of unacceptable toxicities needed to trigger re-evaluation
2	2
3-5	3
6-7	4
5-10	5
11-13	6
14-16	7
17-19	8
20-22	9
23-25	10

Operating characteristics of the stopping rule based on 10000 simulations are shown below.

True probability of	Probability of triggering
unacceptable toxicity	stopping guidelines
5%	0.4%
10%	1.8%
15%	6%
20%	14%
25%	27.5%
30%	44.9%
35%	62.3%
40%	78%
45%	89.2%

REFERENCES

- 1. Rahib, L. *et al.* Projecting cancer incidence and deaths to 2030: the unexpected burden of thyroid, liver, and pancreas cancers in the United States. *Cancer Res.* **74**, 2913–2921 (2014).
- 2. Siegel, R. L., Miller, K. D. & Jemal, A. Cancer statistics, 2016. *CA Cancer J Clin* **66**, 7–30 (2016).
- 3. Burris, H. A. *et al.* Improvements in survival and clinical benefit with gemcitabine as first-line therapy for patients with advanced pancreas cancer: a randomized trial. *J. Clin. Oncol.* **15**, 2403–2413 (1997).
- 4. Conroy, T. *et al.* FOLFIRINOX versus Gemcitabine for Metastatic Pancreatic Cancer. *New England Journal of Medicine* **364**, 1817–1825 (2011).
- 5. Von Hoff, D. D. *et al.* Increased Survival in Pancreatic Cancer with nab-Paclitaxel plus Gemcitabine. *New England Journal of Medicine* **369**, 1691–1703 (2013).
- 6. Borazanci, E. *et al.* Adenosquamous carcinoma of the pancreas: Molecular characterization of 23 patients along with a literature review. *World J Gastrointest Oncol* 7, 132–140 (2015).
- 7. Brahmer, J. R. *et al.* Safety and activity of anti-PD-L1 antibody in patients with advanced cancer. *N. Engl. J. Med.* **366**, 2455–2465 (2012).

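### The two causality categories in Section 7.2 leave out events with plausible timing and a competing cause, so the toxicity stopping rule can under-count them

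*Combined protocol and SAP*

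**What the plan says.** Section 7.2 tells the investigator to judge relatedness by two definitions.

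- No applies when the time course "rules out a causal relationship and another cause (concomitant drugs, therapies, complications, etc.) is suspected".
- Yes applies when the time course fits a causal link and "no other cause (concomitant drugs, therapies, complications, etc.) can be identified".

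Both halves of each definition are required. A list of six considerations follows, introduced by "The following factors should also be considered". Nothing says what to record when neither definition is met.

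The answer matters in several places.

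- Section 5.6 limits all three unacceptable-toxicity items to treatment-related events. Item 1 begins "Any treatment-related > grade 3 AEs", item 2 begins "Treatment related blood bilirubin > 5 x ULN", and item 3 (eye toxicity) carries the same restriction.
- Section 13.4 makes these events the stopping-rule endpoint: their occurrence "at any time during the treatment will be the endpoint for safety monitoring".
- Section 11.2 includes drug-related toxicity counts among the secondary safety endpoints.
- Section 7.5.8.1 requires a 15-day report for unexpected SAEs that are related.

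Other sections use other standards. Sections 5.2.2 and 6.2 define drug-related and immune-related events as ones whose cause is unknown. The 7-day report in Section 7.5.8.1 covers "any fatal or life-threatening adverse event that is unexpected and assessed by the investigator to be possibly" related to the agent, a grade of attribution that Section 7.2 does not contain. The SAE form in Appendix D has separate related/unrelated entries for retifanlimab and for the underlying disease.

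**The concern.** In advanced pancreatic or ampullary cancer, a competing explanation can often be named for a raised bilirubin, raised transaminases or severe diarrhoea: the disease, a biliary stent, another medicine. If naming one is enough to fail Yes, a toxicity that the drug may have caused drops out of the count that triggers a safety re-evaluation. It drops out equally if the field is left blank or marked No.

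With at most 25 patients and boundaries between 2 and 10 events, one or two events decide whether the rule fires. The same attribution feeds the toxicity endpoint and the 15-day reports. If sites resolve the gap differently, the pooled count mixes different definitions.

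**Working it through.** **Step 1. Are the definitions exhaustive?** Cross the two conditions:

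| | No other cause identifiable | Another cause identifiable or suspected |
|---|---|---|
| Timing consistent with the drug | Yes | neither |
| Timing rules the drug out | neither | No |

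Two of the four cells have no category. The upper right cell is the one that matters for safety.

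**Step 2. Reproduce the stopping boundaries.** Inputs from Sections 5.6 and 13.4: prior Beta(1.5, 5.5), threshold 33%, trigger when the posterior probability exceeds 60%. For n patients the boundary is the smallest x with P(p > 0.33 | Beta(1.5 + x, 5.5 + n − x)) > 0.60. This matches Tables 2 and 5 at every n from 2 to 25, provided the row labelled 5-10 is read as 8-10. For example, at n = 8, four events give 0.597 (no trigger) and five give 0.787 (trigger).

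**Step 3. Probability of triggering.** Let b(n) be the boundary and q the chance that a patient has a counted event. Starting from a₀(0) = 1, for n = 1 to 25:

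a_n(x) = a_{n−1}(x)(1 − q) + a_{n−1}(x − 1) q, kept only for x < b(n), with no boundary at n = 1.

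P(trigger) = 1 − Σ a₂₅(x).

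| True rate | Exact | Stated in the protocol |
|---|---|---|
| 20% | 11.7% | 14% |
| 30% | 38.3% | 44.9% |
| 35% | 56.1% | 62.3% |
| 45% | 85.5% | 89.2% |

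A simulation of 200,000 runs at 30% gave 38.3%, agreeing with the recursion. The stated values are therefore not fully reproduced. That is a separate matter; the baselines below are the recomputed ones.

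**Step 4. Effect of missed events.** Let f be the share of truly drug-related unacceptable toxicities not recorded as related. The documents give no value, so f is an assumption. The counted rate is q = p(1 − f); for p = 35% and f = 20%, q = 0.35 × 0.80 = 0.28.

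| True rate | f = 0 | 10% | 20% | 30% | 40% |
|---|---|---|---|---|---|
| 35% | 56.1% | 43.6% | 31.7% | 21.5% | 13.6% |
| 45% | 85.5% | 74.2% | 59.6% | 43.6% | 28.6% |

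**Step 5. The opposite default.** If ambiguous events are entered as related and this raises the counted rate from 20% to 30% (also an assumption), triggering rises from 11.7% to 38.3%.

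**The case against.** A reader might infer that the rule will under-count and that the bias runs towards calling the drug safe. The documents do not support that. An ambiguous event fails No as clearly as it fails Yes, because No needs timing that excludes the drug. With no stated default, an investigator could enter it as related, and Step 5 shows the count could then run high. The six further considerations include underlying disease, concomitant medication and class effect, which suggests weighing causes rather than automatic exclusion. The SAE form accepts attribution to both drug and disease. The 7-day report uses a broader standard, which works against missing fatal or life-threatening events.

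There are other protections. Section 7.5.1 captures all AEs and sends all SAEs to the IND sponsor and the drug supplier whatever their attribution, and Section 12.3 provides for review of safety outcomes and committee oversight. Section 5.6 also exempts many asymptomatic laboratory changes and short-lived diarrhoea, so some of the obvious examples would not count in any case.

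What stands: the direction is not fixed by the text, and the percentages in Step 4 depend on an assumed f. What does not: the further considerations are additional and are not said to override the definitions, several of them direct the investigator to look for alternative causes, and capture of all AEs does not repair a trigger that counts only related ones.

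**Conclusion.** The point holds as a gap that can bias the count, not as a demonstrated bias. Section 7.2 leaves a clinically likely type of event without a category and, read literally, bars it from the only category that counts. The stopping rule, the drug-related toxicity endpoints and the 15-day reports inherit that gap.

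The size cannot be derived from the documents. The illustration shows only that the rule is sensitive: at a true rate of 35%, a missed share of 10% lowers the triggering probability by 12.5 points (56.1 − 43.6), and 40% lowers it by 42.5 points (56.1 − 13.6). These figures assume 25 patients, monitoring after each one, the 8-10 reading of the mislabelled row, and that every event in the missed share goes uncounted. They should not be read as the expected loss, nor 56.1% as the protocol's own figure. Because the gap affects a safety trigger and closing it needs only wording, it should be closed.

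**What to change.** Replace the two definitions in Section 7.2 with exhaustive ones, for example:

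- Related: a reasonable possibility that study drug caused or contributed to the event.
- Not related: timing makes causation implausible, or another cause fully explains the event.
- If unclear: count as related for safety monitoring.

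The last line is a policy choice for the sponsor; the essential thing is that a default is written down. Use the one standard in Sections 5.6, 7.5.8.1, 11.2 and 13.4. Reconcile it with the unknown-cause definitions in Sections 5.2.2 and 6.2, the broader wording for the 7-day report, and the two-column attribution on the Appendix D form. Section 5.9 refers back to Section 5.6 for removal from treatment, so the amendment should also say whether the monitoring default reaches that section; that clinical decision lies outside this point.

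The cost is protocol and CRF wording plus site instruction. The downside is that some disease-related events will be counted, so re-evaluation will trigger more often, by an amount that depends on how many such events occur.
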